
Concomitant Medications and Treatments:
 
Subjects must remain on stable daily dose of prednisone or prednisone equivalent through Week 16 of the study. Taper of corticosteroid is encouraged between Weeks 16 and 24 as clinically indicated.
 
All other background medications for SLE must remain stable throughout the study.
 
No new immunosuppressant therapies or other new treatments for SLE may be initiated during the study.
 
Subjects are not permitted to receive live or live-attenuated vaccines during the study.
 
All medications and nondrug therapies (eg, blood transfusions, oxygen supplementation) taken from 30 days prior to the Screening Visit and throughout the study will be recorded.
	

Study Drug and Treatment Administration:
 
Acthar is a sterile preparation of purified adrenocorticotrophic hormone (ACTH) analogue formulated in a gel for repository administration. Acthar and its matching placebo will be supplied by the sponsor and administered SC as follows in this study:
 
Treatment A: Acthar 1 mL (80 U) administered SC every other day from Week 0 to 4 and 2x/week from Weeks 5 to 24.
 
Treatment B: Placebo 1 mL administered SC every other day from Week 0 to 4 and 2x/week from Weeks 5 to 24.
	

Efficacy Evaluations:
 
The following efficacy assessments will be evaluated: SRI, SLEDAI-2K, BILAG-2004, PGA, Safety of Estrogens in Lupus Erythematosus National Assessment (SELENA) Flare Index (SFI), Cutaneous Lupus Erythematosus Disease Area and Severity Score (CLASI), 28 Joint Count, and prednisone usage after Week 16.
	

Study Title: A Multicenter, Randomized, Double Blind, Placebo Controlled Study to Assess the Efficacy and Safety of Acthar® Gel in Subjects With Persistently Active Systemic Lupus Erythematosus Despite Moderate Dose Corticosteroids	
Protocol Number: MNK14304067	Type: Phase 4 (US)/ Phase 2 (Outside the US)
Condition/Disease:	Systemic Lupus Erythematosus

group as a factor and the baseline value of the corresponding endpoint as a covariate. Mixed model with repeated measurements will be performed as deemed necessary. Secondary and exploratory endpoints that are proportions will be analyzed using Pearson's chi-square test or Fisher's exact tests.
 
[REDACTED]
 
[REDACTED]
 
[REDACTED]
 
[REDACTED]
 
[REDACTED]
 
[REDACTED]
 
[REDACTED]
	

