
Safety Analysis
 
Treatment-emergent adverse events and serious adverse events will be summarized using the MedDRA by preferred term within system organ class.
 
Hospital admissions and the reason for each admission will be listed and summarized descriptively by visit and treatment. The cumulative number of hospital admissions will be compared between treatment groups at Week 24 with a 2-sided Pearson's chi-square test or Fisher's exact test at a significance level of 0.05.
 
Other safety data will be listed and summarized descriptively or graphically, as appropriate.
 
[REDACTED]
 
[REDACTED]
 
[REDACTED]
 
[REDACTED]
	

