17.1.4 SELENA Flare Index

The SFI categorizes SLE flare as mild, moderate or severe based on the following 6 variables (Buyon et al, 2005):

- Change in SELENA SLEDAI score from the most recent assessment to current.
- Change in signs or symptoms of disease activity.
- Change in prednisone dosage.
- Use of new medication for disease activity or hospitalization.
- Change in PGA score.
- Hospitalization for SLE activity.

A severe flare is defined as 1 or more of the following: a) SLEDAI score greater than 12; b) new or worsening CNS involvement, vasculitis, glomerulonephritis, myositis, thrombocytopenia (platelet count < 60,000/mL), or hemolytic anemia (hemoglobin level < 70 g/L or decrease in hemoglobin level > 30 g/L), each requiring doubling of corticosteroid dosage to a final dosage > 0.5 mg/kg per day or acute hospitalization; c) any manifestation requiring an increase in dosage of prednisone or equivalent drug to greater than 0.5 mg/kg per day, or initiation of therapy with cyclophosphamide, azathioprine, mycophenolate mofetil, or methotrexate; d) hospitalization for lupus activity; and e) PGA score greater than 2.5 points.

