21.6 Efficacy Analysis

Subjects will be included in the efficacy analyses based on their treatment assignment. The primary endpoint is the proportion of SRI responders at Week 16. The proportions of SRI responders for the 2 treatment groups will be summarized descriptively by visit and treatment group in tabular format and compared using a 2-sided Pearson's chi-square test at a significance level of 0.05. If the responder or nonresponder count falls to equal or below 5 in either treatment group, 2-sided Fisher's exact test will be used instead. All quantitative secondary and exploratory endpoints will be analyzed using analysis of covariance models with treatment group as a factor and the baseline value of the corresponding endpoint as a covariate. Mixed model with repeated measurement will be performed as deemed necessary. Secondary and exploratory endpoints that are proportions will be analyzed using Pearson's chi-square test or Fisher's exact tests.

For the primary efficacy endpoint, subjects who do not provide data to allow classification as responders will be considered nonresponders, that is, missing data will be imputed as non-responder. A similar approach will be applied to secondary efficacy endpoints that are proportions; missing will be classified as not satisfying the conditions described for that endpoint. A full description of missing data imputation method for all endpoints will be described in the statistical analysis plan.

██
██
██
██
██
██

All subjects who receive at least 1 dose of study drug will be included in the safety analyses.

Adverse events will be coded using MedDRA (version 19.0 or higher) by preferred term within system organ class. The number of AEs and the number of subjects reporting AEs will be listed and summarized descriptively by body system, preferred term, severity, and causality for each treatment group. Only TEAEs (events that are new in onset or aggravated in severity following treatment) will be included in all summaries. SAEs (including death) will be summarized.

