Clinical laboratory tests (hematology, lipid panel, blood chemistry, and urinalysis); [REDACTED] and C3, C4, and anti-ds DNA antibodies results will be listed by subject and summarized by visit and treatment group. Categorical laboratory results will be presented with the frequency and percentage in each category by treatment group. Change from baseline at each visit will also be summarized. Shift tables will be generated if applicable. Select laboratory parameters may be presented graphically. Abnormal laboratory values will be identified and analyzed.

Vital sign results (heart rate, diastolic/systolic blood pressures, respiratory rate, and body temperature) and corresponding changes from baseline values will be summarized at each visit with descriptive statistics by treatment group.

Hospital admissions and the reason for each admission will be listed and summarized descriptively by visit and treatment. The cumulative number of hospital admissions will be compared between treatment groups at Week 24 with a 2-sided Pearson's chi-square test or Fisher's exact test at a significance level of 0.05.

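### The one readable between-arm safety test pools all hospital admissions, so fewer lupus admissions can offset or dilute an excess of admissions for drug harm

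*Combined protocol and SAP*

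**What the plan says.** The synopsis (Safety Analysis) and the hospital-admissions part of the safety analysis (21.8.4 in the table of contents) carry the same rule. First comes description: "Hospital admissions and the reason for each admission will be listed and summarized descriptively by visit and treatment". Then comes a test: "The cumulative number of hospital admissions will be compared between treatment groups at Week 24", to be done "with a 2-sided Pearson's chi-square test or Fisher's exact test at a significance level of 0.05". Neither place limits the tested admissions by cause, and Section 22.2 defines hospitalization as any official admission.

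The rest of the readable safety plan is descriptive. Adverse events "will be listed and summarized descriptively by body system, preferred term, severity, and causality for each treatment group", laboratory tests and vital signs are summarized by visit and arm, and the synopsis closes with "Other safety data will be listed and summarized descriptively or graphically, as appropriate".

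Section 17.1.4 names "Hospitalization for SLE activity" as a variable of the SELENA Flare Index (SFI) and puts "d) hospitalization for lupus activity" among the criteria for a severe flare. The synopsis lists the SFI under efficacy evaluations.

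**The concern.** The trial aims to show that Acthar reduces disease activity (Section 11.1). If it does, admissions for lupus activity should fall. Section 10.5 lists corticosteroid-like reactions, including fluid retention, altered glucose tolerance and raised blood pressure. Section 22.5 follows serious infections, elevated blood pressure and hyperglycemia as events of special interest. Admissions for those reasons could rise.

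A test on the sum cannot separate the two movements. If the drug both works and harms, the pooled difference shrinks and the p-value says little about harm. If the drug only works, a pooled result in its favour would sit in the safety section although it reflects efficacy. Even with no effect on lupus admissions, including them adds events unrelated to harm and weakens the test.

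At stake is the meaning of the one safety p-value in the readable plan. The primary endpoint is not affected.

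**Working it through.** **Inputs from the documents.** 81 randomized per arm (Section 21.11); two-sided 0.05, Pearson or Fisher (21.8.4). The documents give no admission rate, count or power, so every rate below is an assumption.

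**The plan's own figure.** The only stated power is 90% for the primary endpoint: 80 per arm, 30% against 55%. With pooled variance, z = (0.25√80 − 1.96√(2 × 0.425 × 0.575)) / √(0.30 × 0.70 + 0.55 × 0.45) = (2.236 − 1.370)/0.676 = 1.28, so power is 0.8997. The 90% reproduces, but it says nothing about admissions.

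**Method.** The outcome is a subject with at least one admission, because a chi-square or Fisher test needs one yes/no result per subject. With independent causes, P(any) = 1 − (1 − harm)(1 − SLE). Rejection probability is the sum of binomial probabilities over all pairs of counts with p < 0.05, at 81 per arm.

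**Step 1: dilution with no lupus benefit.** Harm 12% Acthar, 3% placebo; SLE 12% in both.
- Any admission, Acthar: 1 − 0.88 × 0.88 = 22.6%.
- Any admission, placebo: 1 − 0.97 × 0.88 = 14.6%.
- Harm-only test rejects 0.59 (Pearson) or 0.49 (Fisher); pooled test 0.25 or 0.19.

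By symmetry, suppose lupus admissions are 3% on Acthar and 12% on placebo, and other admissions are 12% in both arms. The pooled test then rejects in Acthar's favour 0.25 or 0.19 of the time, with no difference in harm.

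**Step 2: offset.** Rates are Acthar vs placebo; rejection probabilities are Pearson / Fisher.

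| Harm | SLE | Any admission | Harm-only | Pooled |
|---|---|---|---|---|
| 12% vs 3% | 6% vs 12% | 17.3% vs 14.6% | 0.59 / 0.49 | 0.07 / 0.05 |
| 12% vs 3% | 3% vs 12% | 14.6% vs 14.6% | 0.59 / 0.49 | 0.05 / 0.03 |
| 15% vs 5% | 5% vs 15% | 19.3% vs 19.3% | 0.58 / 0.49 | 0.05 / 0.03 |
| 6% vs 2% | 2% vs 6% | 7.9% vs 7.9% | 0.23 / 0.11 | 0.05 / 0.03 |

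With an exact offset, only half of the pooled rejections point toward harm.

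**Step 3: single data sets** (Acthar vs placebo, no subject admitted for both causes). Harm 10 vs 2 is a difference of 8/81 = 9.9 points. The pooled proportion is 12/162 = 0.0741, so z = 0.0988/√(0.0741 × 0.9259 × 2/81) = 2.40, giving Pearson p = 0.016 and Fisher p = 0.032.
- Add SLE 5 vs 5: 15 vs 7, p = 0.067 / 0.107.
- Add SLE 4 vs 10: 14 vs 12, p = 0.67 / 0.83.
- Add SLE 2 vs 10: 12 vs 12, p = 1.00.

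**The case against.** The strongest reply is that nothing is hidden. Reasons for admission are to be summarized by arm, so a contrast such as 10 vs 2 and 2 vs 10 would be on the page. Serious adverse events are summarized too, and Section 22.5 follows most of the relevant harms. This stands, and it confines the problem to the test and how it is read.

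A reader might infer that the protocol counts a lupus admission as efficacy failure. It does not go that far. Hospitalization is not part of the SRI (17.2) or of any listed secondary endpoint (21.3.2); it is one severe-flare criterion on the SFI. Section 22.2 also makes worsening lupus reportable once it results in a serious event, and inpatient hospitalization is a seriousness criterion. Lupus admissions therefore have a proper place in a safety count.

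A reader might also infer that this is the plan's only formal safety comparison, or that a null result will be taken as no safety difference. The first holds only for the readable text, since parts of the statistical section are redacted. For the second, no section makes this test a gate or states how a null result will be read.

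Finally, all-cause admission needs no attribution, and flare can be hard to tell from infection or fluid retention. That is a good reason to keep the all-cause line. It is not a reason to leave the by-reason split without an estimate, because the reason is already recorded and SFI scoring already requires the judgment. Low power also stands: with few events a non-lupus test will often miss a real excess, so an interval is more useful than a p-value alone.

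**Conclusion.** The point holds as a minor one. In the readable text, the one between-arm safety test adds admissions that effective treatment should reduce to admissions the drug may cause, so its p-value cannot be read as evidence about harm in either direction.

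The direction of the problem follows from the documents; its size does not. The illustration in Step 1 loses more than half the power with no lupus benefit at all (0.25 against 0.59 by Pearson, 0.19 against 0.49 by Fisher). Exact cancellation is a limiting case, not a forecast. All of this rests on assumed rates, independent causes and counting subjects. The documents do not support the stronger conclusion that a harm signal would go unseen, because the by-reason summary by arm remains.

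**What to change.** Keep the all-cause comparison. In Section 21.8.4 and the synopsis, add two pre-specified between-arm comparisons: subjects with at least one admission not due to SLE activity, and separately subjects with at least one admission for SLE activity. Give each a risk difference and 95% CI. Use the reason already recorded, with the classification fixed before unblinding. Add a sentence that a non-significant all-cause result is not evidence of no safety difference.

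The cost is a few lines of wording and two table rows, with no new data collection. The small downside is reliance on the blinded investigator's attribution, and intervals that will be wide if admissions are rare.

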21.8.5 Other Safety Analysis

Other safety assessments including physical examinations, weight, pregnancy testing, and HbA1c will be listed and summarized descriptively or graphically, as appropriate.

[REDACTED]

[REDACTED]

[REDACTED]

[REDACTED]

[REDACTED]

21.10 Interim Analysis

Blinded aggregate data analyses will be completed when 25%, 50% and 75% of subjects complete Week 16. No other interim analyses are planned for this study.

21.11 Statistical Power and Sample Size Considerations

It is expected that approximately 270 subjects will be screened to randomize a total of 162 subjects into 1 of the 2 treatment groups: 1 mL (80 U) of Acthar every other day for 4 weeks followed by 1 mL (80 U) of Acthar for 20 weeks or 1 mL of placebo every other day for 4 weeks followed by 1 mL of placebo 2 times per week for 20 weeks in a 1:1 ratio (81 per group). The primary efficacy analysis will compare the SRI response rate in the Acthar 1 mL (80 U) group to the SRI response rate in the placebo group. Assuming 2 subjects might not qualify for the mITT analysis population after randomization, with 80 mITT subjects in each treatment group (160 total) and a response rate of 30% in the placebo group and 55% in the Acthar group, the study will have a 90% power to detect a treatment difference at the 0.05 level of significance.

21.12 Deviations From Statistical Analysis Plan

Any deviations from the planned statistical analysis will be described and justified in the final clinical study report as appropriate.

22 ADVERSE EVENTS AND SERIOUS ADVERSE EVENTS

22.1 Safety

For safety information about Acthar refer to the most recent version of the Prescribing Information ([Mallinckrodt, 2015](#)) and the Investigators Brochure ([Mallinckrodt, 2016](#)).

22.2 Definitions

Adverse Event

An AE is any untoward or undesirable medical occurrence in a subject who is administered IMP, which does not necessarily have to have a causal relationship with this treatment.

Examples of AEs include but are not limited to:

- Clinically significant laboratory findings.
- Clinically significant changes in physical examination findings.
- An AE occurring due to IMP overdose whether accidental or intentional.
- An AE occurring from IMP abuse.
- An AE associated with IMP withdrawal.
- Unexpected Adverse Event.

An unexpected AE is defined as an AE, the nature and severity of which is not consistent with the applicable product information in the most recent version of the Investigator's Brochure.

SLE Activity Changes

All changes in SLE activity that are unequivocally due to progression of disease should not be reported as an AE unless they result in a SAE as defined below.

Serious Adverse Event

An SAE is defined as any untoward medical occurrence that at any dose results in any of the following outcomes:

- Death.
- A life-threatening AE.
- Inpatient hospitalization or prolongation of existing hospitalization.
- A persistent or significant incapacity or substantial disruption of the ability to conduct normal life functions.
- Results in a congenital anomaly/birth defect.

Important medical events that may not result in death, be life-threatening, or require hospitalization may be considered serious when, based upon appropriate medical judgment, may jeopardize the subject or subject and may require medical or surgical intervention to prevent one of the outcomes listed above. Examples of such medical events include allergic bronchospasm requiring intensive treatment in an emergency department or at home, blood dyscrasias or convulsions that do not result in inpatient hospitalization, or the development of drug dependency or drug abuse.

Death

Death is an outcome of an event. The event that resulted in death should be recorded and reported on the SAE Form. All causes of death must be reported as SAEs. The investigator should make every effort to obtain and send death certificates and autopsy reports to Mallinckrodt.

Life-Threatening Event

A life-threatening event refers to immediate risk of death as the event occurred per the reporter. A life-threatening event does not include an event that, had it occurred in a more severe form, might have caused death but, as it actually occurred, did not create an immediate risk of death. For example, hepatitis that resolved without evidence of hepatic failure would not be considered life-threatening, even though hepatitis of a more severe nature can be fatal. Similarly, an allergic reaction resulting in angioedema of the face would not be life-threatening, even though angioedema of the larynx, allergic bronchospasm, or anaphylaxis can be fatal.

Hospitalization

Hospitalization is defined as an official admission to a hospital. Hospitalization or prolongation of a hospitalization constitutes a criterion for an AE to be serious; however, it is not in itself considered an SAE. In absence of an AE, a hospitalization or prolongation of a hospitalization should not be reported by the investigator as an SAE. Such situations include, but are not limited to, the following:

A hospitalization or prolongation of hospitalization is needed for a procedure required by the protocol.

A hospitalization or prolongation of hospitalization is part of a routine procedure followed by the center (eg, stent removal after surgery). This should be recorded in the study file.

A hospitalization for a preexisting condition that has not worsened.

Note that the following hospitalizations are not considered SAEs in Mallinckrodt clinical studies:

A visit to the emergency department or other hospital department of less than 24 hours that does not result in admission (unless considered "important medical event" or life-threatening event).

22.3 Adverse Event and Serious Adverse Event Classifications

Study Drug Relatedness

The following classifications should be used when evaluating the relationship of AEs or SAEs to study treatment (Table 22-1).

Table 22-1: Adverse Event Relationships

Relationship	Definition
Not Related	No relationship between the experience and the administration of study treatment; related to other etiologies such as concomitant medications or subject's clinical state.
Unlikely Related	The current state of knowledge indicates that a relationship is unlikely.
Possibly Related	A reaction that follows a plausible temporal sequence from administration of the study treatment and follows a known response pattern to the suspected study treatment. The reaction might have been produced by the subject's clinical state or other modes of therapy administered to the subject.
Related	A reaction that follows a plausible temporal sequence from administration of the study treatment and follows a known response pattern to the suspected study treatment and can be confirmed with a positive re-challenge test or supporting laboratory data.

Severity Assessment

For purposes of consistency, if required the investigator may use the intensity grades presented in Table 22-2.

Table 22-2: Adverse Event Severity Grades

Grade	Definition
Mild	Does not interfere with subject's usual function and activities
Moderate	Interferes to some extent with subject's usual function and activities
Severe	Interferes significantly with subject's usual function and activities

If an AE increases in severity (eg, from moderate to severe); decreases in severity (eg, changes from moderate to mild); or there is a change in seriousness, a new AE will be opened and the original AE will be closed. If an AE is still ongoing at the time of a subject's completion of the follow-up visit, the resolution/stop date and time is left blank.

To ensure there is no confusion or misunderstanding of the difference between the terms "serious" and "severe," which are not synonymous, the following note of clarification is provided:

The term "severe" is used to describe the intensity (severity) of a specific event (as in mild, moderate, or severe myocardial infarction); the event itself, however, may be of relatively minor medical importance (such as a severe headache). This is not the same as "serious," which is based on the subject/event outcome or action criteria usually associated with events that pose a threat to a subject's life or functioning. Seriousness (not severity) serves as a guide for defining regulatory reporting obligations.

22.4 Adverse Event and Serious Adverse Event Recording and Reporting

AEs and SAEs will be recorded from signing of the ICF through completion of the Follow-up Visit. The investigator is required to record the AE or SAE regardless of the severity of the event or its relationship to study treatment. The investigator must follow up on all AEs and SAEs reported to have occurred through the Follow-up Visit until the event has resolved or stabilized or at such time the investigator refers the subject to a nonstudy physician. The investigator will document the further follow-up information in the subject's source document.

During the period specified above, the investigator will:

- Record all AEs and SAEs from the signing of the ICF through the completion of the Follow-up Visit.
- Report all SAEs on an SAE Report Form to Global Pharmacovigilance.
- Report all pregnancies to Global Pharmacovigilance on the Pregnancy Surveillance Form.
- Submit any Expedited Safety Report or Suspected Unexpected Serious Adverse Reaction from Global Pharmacovigilance to the IRB/IEC.

The reporting requirements for AEs are summarized in Table 22-3.

Table 22-3: Reporting Requirements for Adverse Events

Seriousness	Reporting Time	Type of Report
All Serious	Within 24 hours of first knowledge of event	Initial report on the SAE Form, appropriate eCRF, and source document
	Within 24 hours of receipt of follow-up information	Follow up report on the SAE Form, appropriate eCRF, and source document
Nonserious	Per case report form submission procedure	Appropriate eCRF and source document

Adverse Events

Adverse events can be reported spontaneously or elicited during open-ended questioning (ie, "How have you been feeling since your last visit?"), examination, or evaluation of a subject. Signs and symptoms must be recorded using standard medical terminology. For subjects incapable of giving consent, the legally acceptable representative may provide information regarding the subject's status.

All fields on the AE CRF page should be completed for each event with a full description of the event and date of onset/start and resolution/stop. A medical diagnosis if known, should be recorded in lieu of each individual sign and symptom associated with the diagnosis and experienced by the subject. If no medical diagnosis is known, the term used by the subject to describe the event or signs noted by the site personnel should be recorded.

Serious Adverse Events

Initial Reporting

Serious adverse events (based on FDA/ICH definition of an SAE) require immediate reporting to Global Pharmacovigilance.

- For all SAEs, the investigator, or designee, must complete the SAE Report Form with the minimum information required by FDA and ICH and fax it to Mallinckrodt at [contact] or email at [contact] within 24 hours of first knowledge of the event even if the experience does not appear to be related to the IMP.
- The investigator, or designee, will receive acknowledgement of receipt of the SAE Report Form from Mallinckrodt.
- Should the investigator or designee have any difficulty in sending the SAE Report, they may contact Mallinckrodt contacts listed in [Section 2.2](#).

- If there is any doubt about whether the information constitutes an SAE, the information is to be treated as an SAE.

The investigator(s) or designee is required to submit the any Expedited Safety Report or Suspected Unexpected Serious Adverse Reaction to the responsible IRB/IEC.

The sponsor will ensure that any Expedited Safety Report or Suspected Unexpected Serious Adverse Reaction are submitted to the FDA and other regulatory agencies as appropriate.

Follow Up Reporting

The investigator or designee must complete an SAE Report Form for all follow-up information received and fax or e-mail it to Mallinckrodt at [contact] or [contact] within 24 hours of receipt. The investigator(s) or designee will receive acknowledgement of receipt for each SAE Report Form from Mallinckrodt.

- The investigator or designee is required to provide all related information/supporting documentation of an SAE until the SAE is resolved or stabilized or the subject has been referred to a nonstudy physician for follow-up treatment.

The investigator(s) or designee is required to submit the Safety Alert to the responsible IRB/IEC.

The sponsor will ensure that any Expedited Safety Report or Suspected Unexpected Serious Adverse Reaction are submitted to the FDA and other regulatory agencies as appropriate.

